8.9.4 Analysis of Exploratory PD Endpoints

The analysis of exploratory PD endpoints will be based on the FAS.

The primary efficacy analysis will be repeated for each continuous exploratory PD endpoint. Further explanatory variables may be included in the modeling depending on the relevance to the endpoint analyzed and will be specified in the SAP.

8.10 SAFETY AND TOLERABILITY

Safety and tolerability will be assessed by clinical review and summaries of the following parameters:

1. AEs
2. Clinical laboratory test results
3. Physical examination results
4. LISSAs
5. ECG results
6. ISRs
7. Changes and percent changes in total cholesterol, HDL cholesterol, LDL cholesterol, and triglycerides
8. Vital signs

All safety and tolerability analyses will be conducted using the Safety Set.

8.10.1 Adverse Events

AEs, including SAEs, will be coded using the MedDRA. The number and percentage of subjects experiencing an AE will be summarized for each system organ class (SOC) and preferred term (PT) by treatment group. In addition, AEs will be tabulated according to severity, causality, and relation to the study drug.

All AE summaries will be restricted to TEAEs only, defined as AEs that commence on or after the time of start of first study-drug administration and before 30 days after the last dose of blinded drug. AEs without an onset date or time will be defined as treatment emergent, except if an incomplete date (e.g., month and year) clearly indicates that the event started prior to the start of first administration of study drug or if the AE stop date indicates that the event started or stopped prior to the start of first administration of study drug.

For the summaries of AEs, subjects who experience the same AE (in terms of the MedDRA preferred term) more than once will be counted only once for that event. Separate summaries will be provided for AEs by severity, causality, and relationship to study drug.

All AEs will be listed. SAEs will be summarized and listed.

8.10.2 Clinical Laboratory Evaluations

The values and percentage changes from Baseline at Week 12 of total cholesterol, HDL cholesterol, and LDL cholesterol will be summarized.

Observed values and absolute changes from Baseline for routine chemistry, hematology, and urinalysis values will be summarized at each per-protocol time point for each treatment group and overall. Shift tables may also be presented for select chemistry and hematology parameters, as identified in the SAP.

In data listings, laboratory values will be compared to normal ranges; out-of-range and clinically significant laboratory values will be identified.

8.10.3 Physical Examinations

Physical examination results will be listed for each subject.

8.10.4 Vital Signs

Observed values as well as changes from Baseline will be summarized for all vital-sign parameters, by time point and treatment group.

8.10.5 Pregnancy Test

Urine and serum pregnancy test data will be listed for each female subject.

8.10.6 Electrocardiogram

Observed values as well as changes from Baseline will be summarized for all ECG parameters, by time point and treatment group.

8.10.7 Injection-Site Reactions

Frequency tabulations of ISRs will be presented at each time point by treatment group.

8.10.8 Prior and Concomitant Medications

Non-study medications will be classified as prior and concomitant, and coded using the current version of the World Health Organization Drug Dictionary Enhanced (WHO-DD). Prior medications are defined as those taken at least once during the 28 days before Screening. Concomitant medications are defined as those taken at least once from 28 days prior to Screening through the EOS visit. Medications stopped in the 28 days prior to the Screening time point will not be considered concomitant.

Prior medications and concomitant medications will be listed separately. In addition, concomitant medications will be summarized by Anatomical Therapeutic Chemical (ATC)

class and PT using frequency counts and percentages. For the summaries of concomitant medications, subjects who take the same medication (in terms of PT) more than once will be counted only once for that medication.

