Number of Subjects:	Approximately 60 subjects will be randomized.
Number of Study Sites:	Approximately 40–45 sites worldwide.
Test Product(s), Dose, and Mode of Administration:	The NGM282 final product will be supplied in pre-filled syringes intended to deliver 0.3 mL of 1 mg NGM282, 3 mg of NGM282, or placebo for SC injection. Subjects will be instructed to self-administer SC injections of study drug at approximately the same time in the morning.
Duration of Treatment:	Patients will sign the ICF at or prior to the Screening Visit, and will undergo screening assessments to verify eligibility for the study (up to 6 weeks). All subjects will be treated with NGM282 or placebo for 12 weeks, and will be monitored after completing their final dose of NGM282 or placebo (4 weeks). The total duration of individual participation will be approximately 22 weeks.

Criteria for Evaluation: Safety	Safety and tolerability will be assessed by monitoring adverse events (AEs) and concomitant medications; conducting local injection-site symptom assessments (LISSAs), physical examinations (PEs), and 12-lead electrocardiograms (ECGs); measuring vital signs; and collecting clinical laboratory assessments.
Criteria for Evaluation: Pharmacokinetics	Pharmacokinetics (PK) will be analyzed to determine the steady-state trough and 2-hour post-dose NGM282 levels in PSC patients and to compare to the levels in normal volunteers and in patients with other medical conditions (primary biliary cirrhosis, nonalcoholic steatohepatitis [NASH], and type 2 diabetes [T2D]), and to explore PK/PD correlations in terms of drug efficacy, toxicity, and other parameters of the disease activity.

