Criteria for Evaluation: Efficacy & Pharmacodynamics	
The primary efficacy endpoint for this study will be the mean change in ALP in patients with confirmed PSC after 12 weeks of treatment.
 
The following secondary endpoints will be investigated:
 
Efficacy and PD
 
 Percent change from Baseline at Week 12 in ALP Changes and percent changes from Baseline at Week 12 in 
 ALT, AST, bilirubin (total, direct), and GGT C4 and serum bile acids Bile-mediated absorption as measured by fat-soluble vitamins and fecal fat content Changes in pruritus and fatigue, as measured by the weekly mean of the daily Numeric Rating Scale scores Incidence and severity of IBD-associated intestinal symptoms Incidence and severity of acute cholangitis 
Changes in cholestatic symptoms, safety, and tolerability
 
 Safety and tolerability of NGM282 in subjects with PSC with 12 weeks of treatment though the prevalence of AEs, LISSA results, changes in clinical safety laboratory assessments, changes in vital signs, changes in ECGs, changes in physical examination, and the prevalence of concomitant medications The absolute and percentage changes from Baseline at Week 12 of total cholesterol, HDL cholesterol, and LDL cholesterol 
Pharmacokinetics
 
 The exposure of 1 mg and 3 mg of NGM282 in subjects with PSC after 12 weeks of treatment 
Exploratory pharmacodynamics
 
 [REDACTED]

Statistical Methods:	
The primary efficacy analysis will consist of comparing each NGM282 treatment group against the placebo group, within a mixed-effect model repeated measures analysis of the primary efficacy endpoint.
 
The primary efficacy analysis will be repeated for each continuous secondary efficacy endpoint.
 
The categorical secondary efficacy endpoints will be analyzed using confidence intervals of treatment differences.
 
The safety and tolerability endpoints will be summarized.
 
At the planned interim analysis, the evidence regarding the safety and efficacy of NGM282 in the PSC indication will be assessed, in order to evaluate the appropriateness of continuing the study.

----------------------	---

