C4 = 7-alpha-hydroxy-4-cholesten-3-one; CA19-9 = carbohydrate antigen 19-9; ELF = enhanced liver fibrosis; EOS = End of Study; EOT = End of Treatment; ERCP = endoscopic retrograde cholangiopancreatography; HIV = human immunodeficiency virus; IBD = inflammatory bowel disease; INR = International Normalized Ratio; LISSA = local injection-site symptom assessment; MRCP = magnetic resonance cholangiopancreatography; NRS = Numeric Rating Scale; p-ANCA = perinuclear anti-neutrophil cytoplasmic antibodies; PK = pharmacokinetic; Wk = week.

^a There must be a minimum of 14 days between Screening and Day 1 visits for adequate separation of the repeated Chemistry (liver function tests) and INR assessments.

^b Colonoscopy will be performed only in patients with concomitant IBD and who do not have a colonoscopy available within 12 months of Screening.

^c MRCP will be performed in all subjects at Screening.

^d LISSA evaluations will be performed pre-dose for all on-treatment visits.

^e PK blood samples will be collected before subjects dose themselves in the clinic (pre-dose). At Day 1 and Week 12, an additional PK blood sample will be collected 2 hours post-dose.

^f NRS Itch/Fatigue will be completed as a daily diary during Day 1 and Study Weeks 1, 4, and 12. Diary will be dispensed at the study visit prior to the collection week.

^g Mayo Partial IBD Score will be collected in all patients, independent of whether they have IBD or not.

^h A second CA19-9 sample may be collected during the Screening period a minimum of 4 weeks from the original Screening sample in order to meet Inclusion Criteria 3g.

ⁱ A serum pregnancy test will be performed on all female subjects at Screening, Week 12, and Week 16. A urine pregnancy test will be performed on all female subjects at Day 1 (pre-dose).

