6.1. Prior and Concomitant Medications

All medications used within 4 weeks prior to the date of screening and during the study period, as well as the reason for use, will be collected on the source documents and the CRF. Non-study medications will be classified as prior and concomitant, and coded using the current version of the World Health Organization Drug Dictionary Enhanced (WHO-DD).

Prior medications are defined as those taken at least once during the 28 days before Screening. Concomitant medications are defined as those taken at least once from 28 days prior to Screening through the EOS visit. Medications stopped in the 28 days prior to the Screening time point will not be considered concomitant.

The total number of concomitant medications and the number and percentages of subjects with at least one concomitant medication will be summarized by treatment group. The number and percentages of all concomitant medications will be summarized by treatment group, Anatomical Therapeutic Chemical (ATC) class and preferred term. Subjects who take the same medication (in terms of PT) more than once will be counted only once for that medication. All summaries will be performed using the Safety Set.

Prior medications and concomitant medications will be listed.

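### The concomitant-medication table counts drugs used only in Screening and stopped before Day 1, so it does not isolate use after first dose or line up with the TEAE window

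*Protocol*

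**What the plan says.** Protocol 8.10.8 and SAP 6.1 define the term identically: "Concomitant medications are defined as those taken at least once from 28 days prior to Screening through the EOS visit". One exception follows: "Medications stopped in the 28 days prior to the Screening time point will not be considered concomitant". Taken together, the rule is any use from Screening to the end-of-study visit. Neither the first nor the last dose enters it. Prior medications are those used in the 28 days before Screening, so a drug both started and stopped within Screening is not prior and can only be concomitant.

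SAP 6.1 then plans the table: "The number and percentages of all concomitant medications will be summarized by treatment group", by ATC class and preferred term, on the Safety Set, with each subject counted once per preferred term. Neither section plans an on-treatment subset.

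The protocol synopsis gives the measure a safety role. It lists "the prevalence of concomitant medications" with the safety and tolerability endpoints and names concomitant medications among the safety evaluation criteria.

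Screening may last up to six weeks. Its lower limit is in the footnotes to the protocol's Schedule of Study Procedures: "There must be a minimum of 14 days between Screening and Day 1 visits". Randomization is on Day 1 (Protocol 4 and 8.2). AE summaries are restricted to events starting from first dose until 30 days after the last dose (Protocol 8.10.1, SAP 8.1).

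**The concern.** A by-arm medication table is useful in a safety review if it shows whether subjects on active drug needed more additional treatment than those on placebo. Drug use that ended before randomization cannot be an effect of treatment. Counting it adds the same expected amount of noise to every arm and pulls the percentages together.

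The table also cannot be read directly beside the TEAE tables, because the two start at different times. Counting each subject once per preferred term means the mixing cannot be undone from the table: someone who used a drug only in Screening looks the same as someone who needed it on study drug.

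The arms are small. The target is 20 randomized per arm. The supplied SAP describes the interim analysis, which Protocol 8.10.9 sets at a minimum of 8 completers per arm. At 8 subjects, one Screening-only user moves a cell by 1/8 = 12.5 percentage points.

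**Working it through.** **1. The window.** Inputs from the protocol: Screening 14 to 42 days (synopsis; schedule footnote), treatment 12 weeks = 84 days (synopsis), end-of-study visit 4 weeks = 28 days after the last dose (5.6.8). The plan's own figure is reproduced first: 6 + 12 + 4 = 22 weeks, which agrees with "The total duration of individual participation will be approximately 22 weeks".

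| | Longest Screening | Shortest Screening |
|---|---|---|
| Window counted (days) | 42 + 84 + 28 = 154 | 14 + 84 + 28 = 126 |
| Before first dose | 42/154 = 27% | 14/126 = 11% |
| After last dose | 28/154 = 18% | 28/126 = 22% |

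These are shares of calendar time, not of medication use. A window from first dose to end of study would be 84 + 28 = 112 days, close to the TEAE window.

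**2. Effect of Screening-only use.** Let p be the proportion of an arm using a given drug on or after first dose. Let q be the proportion with use confined to Screening as far as the pre-dose period goes (taken then, stopped before Day 1), equal across arms in expectation and independent of later use. Then

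- counted proportion = p + (1 − p)q
- counted difference = (p1 − p0)(1 − q)

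The documents give neither p nor q. The values below are assumptions: p1 = 30%, p0 = 10%, and q from 5% to 30%.

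| q | Active | Comparator | Difference (points) | Ratio |
|---|---|---|---|---|
| 0 | 30% | 10% | 20 | 3.0 |
| 5% | 33.5% | 14.5% | 19 | 2.31 |
| 10% | 37% | 19% | 18 | 1.95 |
| 20% | 44% | 28% | 16 | 1.57 |
| 30% | 51% | 37% | 14 | 1.38 |

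With 20 per arm, the undiluted difference is 0.20 × 20 = 4 subjects. It becomes 0.19 × 20 = 3.8 at q = 5% and 0.14 × 20 = 2.8 at q = 30%.

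**3. Use after the last dose.** This follows randomization, so it need not be equal across arms. If 20% of the active arm and 5% of placebo had use only after the last dose, the counts would be 0.30 + 0.70 × 0.20 = 44.0% and 0.10 + 0.90 × 0.05 = 14.5%. The difference is then 29.5 points, wider than the 20 points on drug. The (1 − q) argument does not carry over to this period.

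**The case against.** The best defence is that little depends on this table. It is descriptive, with no test. Concomitant medication is not among the eight parameters in Protocol 8.10 or the seven in SAP section 8, although the synopsis names it. Tolerability is measured more directly elsewhere: TEAEs by arm, relationship and severity, gastrointestinal events down to lowest level term, and the Mayo partial score at every visit. All medications are also listed. Protocol 5.7 asks subjects to avoid new or changed medication from 4 weeks before Day 1 to end of study, which should keep q small. The supplied SAP is for the interim analysis, and its section 10 mentions a full-study SAP that may treat this differently.

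Most of this stands and sets the severity. It does not remove the misclassification. The restriction in 5.7 starts 4 weeks before Day 1 while Screening may start at Day −42, so a drug stopped between Days −42 and −29 complies with it and is still counted. The protocol itself carries the same definition, whatever a later SAP says.

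A reader might go further and infer three things that the documents do not support:

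- That the table says nothing about use on study drug. All such use is counted; it is only not separable.
- That 45% of the window (70/154 days) is wrongly included. That is the maximum; with the shortest Screening it is 42/126 = 33%. Both figures include the 28 follow-up days, which broadly match the TEAE window and are not a clear defect.
- That a known tolerability signal would be hidden. The diarrhea rates quoted from the earlier PBC study in Protocol 2.4 are adverse-event rates, not medication use, and nothing in the documents allows q to be estimated.

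**Conclusion.** The concern holds for pre-dose use. The stated rule classifies Screening-only drugs as concomitant with study drug, and the SAP repeats it. The expected shrinkage of an arm difference is the factor (1 − q), which rests on Screening-only use being equal across arms in expectation (assured by randomization) and independent of later use (assumed). The shift from 20 points to between 19 and 14 is an illustration over an assumed range, not an estimate for this trial. Severity is minor: the effect is confined to one descriptive safety table, and the primary analysis, sample size and type I error are untouched.

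**What to change.** In Protocol 8.10.8 and SAP 6.1:

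- Define prior medications as those stopped before the first dose.
- Define concomitant medications as those taken at least once on or after the first dose through the end-of-study visit, including drugs started earlier and continuing.
- Flag drugs started after the last dose separately.
- Add a by-arm Safety Set table, by ATC class and preferred term, of medications newly started on or after the first dose.
- Keep Screening-only use in the listings.

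The cost is a wording change and one extra table. It relies on medication start and stop dates, which the present exception for drugs stopped before Screening already implies, though neither section says outright that they are recorded. A table of dose increases is not requested, because the documents do not say that the dose data it would need are collected.

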8.10.9 Interim Analysis

An unblinded interim analysis (IA) will be conducted when approximately 24 subjects (a minimum of 8 subjects per arm) have completed the Week 12 visit. At the IA, the evidence regarding the safety and efficacy of NGM282 in the PSC indication will be assessed, in order to evaluate the appropriateness of continuing the study.

A separate SAP for the IA will be generated, describing the conduct of the IA in detail.

8.11 PHARMACOKINETICS

The following PK parameters will be calculated using the PK Set and the validated PK software, Phoenix WinNonlin, Version 5.3 (or higher; Certara Corporation; Princeton, NJ, U.S.):

- Day 1; Weeks 1, 2, 4, 8, and 12: trough concentration (C_{trough})
- Day 1 and Week 12: C_{trough} ; concentration at 2 hours post-dose ($C_{2\text{h post-dose}}$)

PK data will be used to evaluate the accumulation of NGM282 in the plasma of PSC patients following multiple-dose administration at 1 and 3 mg per day. This will be done by comparing the steady-state trough NGM282 levels in PSC subjects to results obtained on Day 1 in the same subject and, more generally, in the dosing cohort. In addition, determination of NGM282 concentrations 2 hours post-dose on Day 1 and Week 12 will enhance information obtained on accumulation and provide an indication of expected maximum drug concentration (C_{max}) in patients. This information will be directly compared to Phase 1 results obtained in healthy volunteers ([Study 12-0101](#)) and with other medical conditions (PBC, nonalcoholic steatohepatitis [NASH], and T2D). In addition, PK data will be used to explore PK/PD correlations in terms of drug efficacy and toxicity, where data allow. Actual sample times will be used in the data analysis.

The exposure of 1 mg and 3 mg of NGM282 will also be evaluated.

9 DATA MANAGEMENT AND ELECTRONIC SYSTEMS

9.1 DATA MANAGEMENT

A data validation manual (DVM) will specify all relevant aspects of data processing and handling for the study, including how data will be managed and cleaned. Relevant sections of the DVM includes the following: standard operating procedures to be followed; eCRF data entry and flow, tracking and filing; coding and coding review plan; reconciliation of

SAEs; external and vendor data integration, import, and reconciliation; and general listing review.

9.2 ELECTRONIC SYSTEMS

Electronic systems used to collect and process data in this study will include the following:

- Contracted CRO's [REDACTED] randomization and dispensing study-drug supply
- Medidata Rave for general data capture
- PreClarus – real-time study data and analysis
- Statistical Analysis Software (SAS) – data reconciliation/packaging and statistical analysis and review

10 ADMINISTRATIVE ASPECTS

10.1 PROTOCOL ADHERENCE

The PI must adhere to the protocol as detailed in this document and agree that the Sponsor must approve any changes to the protocol prior to seeking approval from the EC.

No alterations in the protocol will occur without agreement between the Sponsor and the PI. No alterations in the protocol affecting subject safety will occur without the express written approvals of the Sponsor, PI, and EC.

10.2 DISCLOSURE

All information provided regarding the study as well as all information collected/documentated during the course of the study will be regarded as confidential. The PI agrees not to disclose such information in any way without prior written permission from the Sponsor.

Any publication of the results either in part or in total (articles in journals or newspapers, oral presentations, abstracts, etc.) by the PI or their representative(s) shall require prior notification and review within a reasonable time frame by the Sponsor and cannot be made in violation of the Sponsor's confidentiality restrictions or to the detriment of the Sponsor's intellectual property rights.

10.3 MONITORING

The Sponsor's or designee's monitor (i.e., "the monitor") will be responsible for monitoring this clinical trial. The monitor will review the study conduct, proper eCRF and source documentation completion and retention, and accurate study-drug accountability. To this end, the monitor will visit the study site at suitable intervals and be in frequent contact through verbal and written communication. The PI will grant access to all documents (related to the study and the individual subjects) at any time these are requested by the sponsor or designee. In turn, the monitor will adhere to all requirements for subject confidentiality as outlined in the ICF. The PI and PI's staff will be expected to cooperate

with the monitor, to be available during a portion of the monitoring visit to answer questions, to resolve discrepancies, and to provide any missing information.

10.4 INSTITUTIONAL REVIEW BOARD/ETHICS COMMITTEE

This protocol, the informed consent document, and all relevant supporting data must be submitted to the IRB/EC for approval. IRB/EC approval of the protocol, informed consent document, and any advertisement used to recruit study subjects must be obtained before the study may be initiated.

The PI is responsible for keeping the IRB/EC advised of the progress of the study and of any changes made to the protocol as deemed appropriate but, in any case, at least once a year. The PI is also responsible for notifying the IRB/EC of any reportable AEs that occur during the study.

